- Change from baseline in overall clinical SD score at 4 weeks of treatment with ruxolitinib 1.5% cream applied twice daily

- Change from baseline in each component of the clinical SD score at 4 weeks of treatment with ruxolitinib 1.5% cream applied twice daily (scale, erythema, pruritus)
- Change in overall clinical SD at 6 weeks (i.e., 2 weeks after treatment cessation) from baseline and from 4 weeks
- The frequency, duration, and severity of AEs
- Changes in vital signs
- Changes in laboratory data for hematology, serum chemistry, and urinalysis

Mechanistic (Exploratory) Endpoints

- Determine the molecular cutaneous phenotype of SD at baseline compared with healthy controls, using transcriptomic and proteomic approaches from skin samples acquired by tape-strips
- Identify molecular markers that correlate with disease activity in SD at baseline
- Characterize the change in molecular responses with treatment of topical ruxolitinib 1.5% cream after 4 weeks of treatment
- Identify molecular markers that correlate with treatment response at 4 weeks

STUDY DESIGN OVERVIEW:

This study is an open-label prospective interventional trial. The study will take place at Icahn School of Medicine at Mount Sinai.

The study will include 25 adult patients with moderate-to-severe-SD as well as 20 age- and gender-matched healthy control subjects for comparison. The SD patients will have baseline clinical score of at least 6 using the SD Severity Score in Appendix 1, or an Investigator Global Assessment (IGA) score of at least 3. Enrolled SD subjects will apply topical ruxolitinib 1.5% cream twice daily for 4 weeks. They will return for visits at weeks 2, 4, and 6 following study treatment initiation for repeat clinical assessments, medication reviews, tape-strip, blood and urine sample collections, and monitoring for adverse events.

After providing consent, all subjects will be assessed for study eligibility, which includes a review of the subjects past and current medical conditions, familial medical history and detailed review of past and current medications. SD subjects will also undergo a review of past topical treatments/therapies for SD, and clinical assessments (clinical SD score and IGA).

Subjects who meet inclusion criteria for eligibility may continue with the Baseline Visit (Week 0) or can be scheduled to return for the Baseline Visit within 28 days of the Screening Visit.

SD Subjects:

Seborrheic Dermatitis Ruxolitinib Cream Protocol
Incyte IIR

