To the best of our knowledge, this is the first study to evaluate differences in the transcriptome between SD and healthy subjects. A previous study (19) evaluated a fold-change (FCH) of 5 in IL-10 cell counts with coefficient of variation of 50% when comparing 10 SD subjects to 4 healthy volunteers. Assuming similar variability, a sample size of n = 20 SD subjects and n= 20 controls would provide 90% power at 5% significance to detect FCH>2.65 when comparing IL-10 expression between SD and controls, based on a two-sided unpaired t-test applied to log2-transformed RNA-seq data and fold-changes back transformed.

Demographics and Other Baseline Characteristics

Descriptive statistics of demographics and other baseline characteristics of patients will be summarized. Other baseline characteristics include height, weight, vital signs, duration of SD disease, concurrent diagnoses from medical history and indications for concomitant medication, concomitant medication, and previous SD treatments.

Analysis of Primary Endpoint

The one-sided binomial test will be used to verify the hypothesis that the proportion of patients achieving IGA 0/1 at 4 weeks of treatment with ruxolitinib 1.5% cream applied twice daily is greater than 0.4.

Analysis of Secondary Endpoints

The two-sided Wilcoxon signed-rank test will assess the significance of changes from baseline in:

- IGA score at 4 weeks of treatment
- Components of clinical SD scoring (scale, erythema, and pruritus) at 4 weeks of treatment.

The two-sided paired t-test will assess the significance of changes from baseline in:

- Overall clinical SD scoring at 4 and 6 weeks of treatment.
- Vital signs measured in interval or ratio scale
- Analytes measured in interval or ratio scale from laboratory tests (hematology, serum, chemistry, and urinalysis) at 4 weeks of treatment

The p-values will be adjusted by the Bonferroni method. The frequency, duration, and severity of AEs will be summarized with tables and summary statistics.

Analysis of Mechanistic (Exploratory) Endpoints

The baseline immune and molecular cutaneous profile of SD at baseline compared with healthy controls and the change in the immune and molecular cutaneous profile of SD with treatment will be assessed by MMRM approach. Gene/Protein expression data will be modeled using a mixed effect model with the interaction between tissue type (non-lesional/ lesional / healthy) and timepoint as fixed effects and a random effect for each subject.

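### The detectable fold change of 2.65 for IL-10 does not follow from the stated CV of 50%, and the log2 SD behind it is not given

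*Combined protocol and SAP*

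**What the plan says.** The Mechanistic Endpoint paragraph (Statistical Considerations) takes its variability from an earlier study, reported as a "fold-change (FCH) of 5 in IL-10 cell counts with coefficient of variation of 50% when comparing 10 SD subjects to 4 healthy volunteers". It then states that "n = 20 SD subjects and n= 20 controls would provide 90% power at 5% significance to detect FCH>2.65", for IL-10 expression in SD versus controls. The test named is a "two-sided unpaired t-test applied to log2-transformed RNA-seq data and fold-changes back transformed".

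The control group is set in the Study Design Overview as "20 age- and gender-matched healthy control subjects for comparison". No other calculation is given for that number. Neither the paragraph nor the amendment log states a standard deviation on the log2 scale, a rule for converting the CV, or which group or quantity the 50% describes.

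**The concern.** Group sizes, power, significance level, sidedness, test and scale are all stated. The one missing input is the log2 standard deviation (SD), and that is the input that turns a standardized difference into a fold change. The only guide to it is "Assuming similar variability", pointing back to a CV of 50%. A CV of 50% is moderate on the log2 scale, while 2.65 is a large detectable effect for 20 per group, so the two look incompatible.

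This is the only stated sensitivity for comparing SD with healthy skin, which is a listed secondary objective with exploratory endpoints, and the only numerical support for 20 controls. A null IL-10 result would be read against 2.65. If the true limit is nearer 1.64, that reading understates what the study could have detected. If the log2 SD is really larger than about 1.34, it overstates it.

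**Working it through.** **Inputs, all from the Mechanistic Endpoint paragraph:** 20 versus 20; 90% power; two-sided 5%; unpaired t-test on log2 data; CV 50%; stated result 2.65. Equal SDs in the two groups are my assumption.

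**Step 1. Detectable standardized difference.** The noncentral t with 38 degrees of freedom gives d = 1.052. The normal approximation agrees closely: (1.960 + 1.282) × √(2/20) = 1.025.

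**Step 2. Detectable fold change.** FCH = 2^(1.052 × SD), with SD on the log2 scale.

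**Step 3. What the plan's 2.65 requires.** log2(2.65) = 1.406, so SD = 1.406 / 1.052 = 1.3365. As a lognormal CV this is √(exp((1.3365 × ln 2)²) − 1) = 1.166, or about 117%.

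**Step 4. What a CV of 50% gives.**

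| Reading of 50% | log2 SD | FCH at 90% power | Power at 2.65 |
|---|---|---|---|
| Used directly as the log2 SD | 0.500 | 1.44 | above 99.9% |
| Lognormal, √(ln 1.25)/ln 2 | 0.6815 | 1.64 | above 99.9% |
| Delta method, 0.5/ln 2 | 0.7213 | 1.69 | above 99.9% |
| Gamma, shape 4, √trigamma(4)/ln 2 | 0.7686 | 1.75 | above 99.9% |
| Half of log2 5 | 1.161 | 2.33 | 96.2% |

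Even a lognormal CV of 100% (SD 1.201) gives only 2.40. A simulation of 100,000 datasets agrees: lognormal data with CV 50% give 89.9% power at 1.64, and gamma data with CV 50% give 89.8% at 1.75.

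**Step 5. Could another setting explain it?** With the lognormal SD of 0.6815, a one-sided 5% test gives 1.56, 95% power gives 1.74, and a two-sided 1% level gives 1.83. None comes near 2.65.

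**Step 6. Near-matches.** Three routes come close, and none is valid for the text as written:

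- 50% of the fold change of 5 is a raw SD of 2.5. Taking log2(2.5) = 1.322 as the SD gives 2.62, with 90.6% power at 2.65. The log of a raw-scale SD is not a log-scale SD.
- The earlier study's group sizes, 10 versus 4, with SD 0.6815 give 2.69, with 89.2% power at 2.65. The text claims 20 versus 20.
- Doubling the lognormal SD to 1.363 gives 2.70, with 88.9% power at 2.65. Nothing in the plan supports the doubling.

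**Size of the gap.** At a lognormal CV of 50%, 6 per group gives 89.5% power at 2.65 and 7 per group gives 94.3%. This measures the discrepancy only; it is not a case for fewer controls.

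**The case against.** The best reply is that this is incomplete disclosure rather than a proven slip. The 50% comes from cell counts in a small published study that is not available here, and the plan does not say whether it describes patients, controls, pooled data or the fold change itself. Both printed numbers could be correct with an unstated conversion between them. The log2(2.5) route shows how 5 and 50% might have led close to 2.65.

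Part of this stands: the documents do not show which number is at fault, or how 2.65 arose. It does not rescue the paragraph. No valid conversion that was tried reaches 2.65, and an SD near 1.34 is not variability similar to a CV of 50%.

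A second reply concerns unequal SDs. With equal group sizes it is roughly the root mean square of the two SDs that matters. If one group had SD 0.68, the other would need about √(2 × 1.3365² − 0.6815²) = 1.76 to reach 2.65. The plan suggests nothing of the kind.

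A third is that putting 1.64 in place of 2.65 would carry a cell-count CV over to tape-strip RNA sequencing and replace a cautious figure with an optimistic one. That is fair, and it is why a sourced log2 SD for expression data is the better repair.

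Finally, little depends on the number. The group size is an input to the paragraph and the fold change its output. The planned analysis is a limma mixed model with Benjamini-Hochberg adjustment, so a single-gene t-test at 5% is only illustrative. This stands, and it limits the weight of the point.

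**Conclusion.** The concern holds, as a minor point. From the plan's own inputs, 20 versus 20 has 90% power for a fold change of about 1.64 under a lognormal CV of 50%, against the stated 2.65. Conversely, 2.65 needs more than twice the stated CV. The exact replacement figure depends on the distributional reading and on equal SDs, but the mismatch does not depend on which of the standard readings is chosen.

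The direction is conservative if 50% is right. The claim is optimistic only if the true log2 SD exceeds about 1.34. The primary endpoint, the number of patients and the planned analyses are unaffected.

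**What to change.** Rewrite the Mechanistic Endpoint paragraph so that its variability and its fold change agree:

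1. State the log2 SD assumed for IL-10 expression and its source, preferably expression data from comparable skin samples.
2. If the 50% is kept, say which group and quantity it describes and how the SD was derived from it.
3. Recompute the detectable fold change as 2^(1.052 × SD). An SD of 0.75 gives 1.73, 1.00 gives 2.07, 1.25 gives 2.49 and 1.50 gives 2.99. If a lognormal CV of 50% is confirmed as the right basis for expression data, the figure is about 1.64.

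The SD should not be back-solved from 2.65, since that would only make the paragraph agree with itself.

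The cost is one corrected paragraph. Sample size, primary endpoint and analysis methods do not change.

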RNA-sequencing data will be profiled by Illumina NovaSeq 6000. RNA-sequencing data will be pre-processed using standard quality control metrics, such as FastQC and MultiQC, sequence alignment by STAR RNA-sequencing aligner and sequencing reads assignment to genomic features by featureCounts, followed by *voom*-transform. Mixed effect models will be used on R's limma framework and p-values for the moderated t-tests and paired-t-test will be adjusted by Benjamini-Hochberg procedure. Extensive bioinformatics tools will be employed to gain insights into the results. This will include (but will not be limited to) pathway and gene-set enrichment analyses by R package GSVA (Gene Set Variation Analysis) and by eXploring Genomic Relations (XGR) that uses prior biological knowledge and relationships from public databases.

We will perform proteomic biomarker studies in serum using the OLINK high-throughput proteomic platform, with the Explore panel that evaluates >1,500 protein analytes. Protein expression data will be modeled using a MMRM approach, with the interaction of study group (treatment /control) and timepoint as fixed effects and a random effect for each subject.

We will use the Spearman coefficient to correlate: 1) molecular markers with disease activity in SD at baseline; 2) changes from baseline in molecular markers with changes from baseline in IGA and overall clinical SD scoring at 4 weeks of treatment.

Data Transfer and Management

Data including the patient info, demographics, clinical scores and treatment allocation code will be sent to our Biostatistical Team in password-protected files.

Data from the [name] Lab (where all mechanistic studies will be done), including sequencing data and proteomics will be deposited in the Mount Sinai Box, which has the necessary safeguards for protection of human subjects research.

All data management steps taken to reformat and merge the clinical and laboratory data will be carried out using R codes, so all the steps of the processes can be reproduced.

Management of the Analysis

Analyses will be run in our desktops, with a backed-up copy in the Mount Sinai Box account. Once the analysis is finalized, all data will be deposited into the central file storage system (CFS), which is accessible to all research members. Both Mount Sinai Box and the CFS have backup capabilities and are encrypted and password protected.

Analysis of Safety and Tolerability

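### The mechanistic power statement uses an unadjusted 5% level for IL-10, but the planned RNA-seq analysis applies Benjamini-Hochberg without exempting IL-10, and the SD behind the figure is not stated

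*Combined protocol and SAP*

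**What the plan says.** Under Statistical Considerations, Mechanistic Endpoint, the plan starts from an earlier immunohistochemistry study reporting a "fold-change (FCH) of 5 in IL-10 cell counts with coefficient of variation of 50" per cent. It carries that variability over to RNA-seq and claims that its design "would provide 90% power at 5% significance to detect FCH>2.65 when comparing IL-10 expression between SD and controls". The group sizes behind this claim are "n = 20 SD subjects and n= 20 controls", and the test is a two-sided unpaired t-test on the log2 scale. No log2 SD is given, and no multiplicity adjustment is mentioned.

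Under Analysis of Mechanistic (Exploratory) Endpoints, gene expression is analysed with mixed models in limma, and "p-values for the moderated t-tests and paired-t-test will be adjusted by Benjamini-Hochberg procedure". IL-10 is not named there, either as a stand-alone test or as an exception. The false discovery rate, the number of genes tested and the share of genes expected to differ are not given.

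The Endpoints section labels the comparison with healthy controls exploratory. The Objectives section lists the same comparison as secondary.

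**The concern.** A power statement describes the planned study only if it uses the test and level that the analysis will use. At a 5% false discovery rate, the Benjamini-Hochberg cut-off for raw p-values is 0.05 times the fraction of tested genes declared significant. It equals 0.05 only if every gene is declared. As the plan is written, IL-10 would therefore face a stricter cut-off than the one assumed in sizing.

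This paragraph is the only numerical support for the number of controls, who give blood, urine and tape strips. A reader should be able to tell from it which fold change the planned analysis can detect.

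**Working it through.** **1. Reproducing the plan's figure.** From the Mechanistic Endpoint paragraph: 20 vs 20, two-sided 5%, 90% power, fold change 2.65, CV 50%. Power comes from the noncentral t distribution with 38 df and noncentrality d × √(20×20/40) = 3.162d, where d is the log2 difference divided by the log2 SD.

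- 90% power needs d = 1.052. Since log2(2.65) = 1.406, the implied SD is 1.406/1.052 = 1.34, which is a log-normal CV of about 117%.
- CV 50% read log-normally gives SD = √ln(1 + 0.5²)/ln 2 = 0.68. The fold change with 90% power is then 2^(1.052 × 0.6815) = 1.64, and power at 2.65 exceeds 99.99%.
- Of the other readings tried, only SD = log2(0.5 × 5) = 1.32 comes close (power 90.6%, detectable fold change 2.62). That is not a standard conversion of a CV.

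The stated figure therefore does not follow from CV 50% by the usual conversion. Both SDs are carried forward.

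**2. Cut-off under Benjamini-Hochberg.** Assumptions not in the documents: false discovery rate q = 5%, independent genes, a share π of genes truly different, all with the same effect. With average power P among the changed genes, the raw cut-off is a = qπP / [1 − q(1 − π)]. Example at SD 1.34 and π = 10%: P = 0.564 gives a = 0.05 × 0.10 × 0.564/0.955 = 0.00295, and power at that cut-off is again 0.564.

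**3. Power at fold change 2.65, SD 1.34.**

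| Share of genes differing | Raw cut-off, 20 vs 20 | Power, 20 vs 20 | Power, 25 vs 20 |
|---|---|---|---|
| 20% | 0.0071 | 68% | 76% |
| 10% | 0.0030 | 56% | 66% |
| 5% | 0.0012 | 44% | 54% |
| 1% | 0.0001 | 18 to 19% | 28% |

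Simulation of the full procedure with 15,000 genes agrees to within about a point. At 30% and 50% of genes differing, power at 20 vs 20 is about 75% and 82%. The moderated t recovers some of the loss: with unlimited degrees of freedom at the same 20 vs 20 cut-offs, power runs from 74% down to just under 30%.

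**4. Power at fold change 2.65, SD 0.68, 20 vs 20.** Power is about 96% if 0.1% of genes differ, 99% at 1% and over 99.9% at 10%. It stays at 90% down to a per-test level of about 0.00001. It falls below 90% (81 to 86% for 10,000 to 20,000 genes) only if IL-10 is practically the sole true signal.

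**5. Fold change with 90% power after adjustment, 20 vs 20.** Put P = 0.9 in the formula in step 2, so that the changed genes sit at the fold change being sought.

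| Share differing | Raw cut-off | SD 1.34 | SD 0.68 |
|---|---|---|---|
| Single 5% test | 0.05 | 2.65 | 1.64 |
| 20% | 0.0094 | 3.3 | 1.8 |
| 10% | 0.0047 | 3.6 | 1.9 |
| 5% | 0.0024 | 3.9 | 2.0 |
| 1% | 0.0005 | 4.6 | 2.2 |

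**6. Group sizes.** Baseline tape strips are taken at Visit 2, before any dropout, so the planned baseline comparison is 25 vs 20 (noncentrality 3.333d, 43 df). At SD 1.34, a single 5% test then has 90% power at a fold change of 2.51.

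**The case against.** The sizing sentence states its transcript, test, sidedness and level, and it claims no genome-wide power. Sizing an exploratory omics comparison on one illustrative marker is common. That stands: the issue is a mismatch between sizing and analysis, not an error within the sentence's own test.

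A reader might go further and infer that the planned analysis fails to deliver 90% power at 2.65. The documents do not establish that. With the plan's CV of 50% converted in the usual way, power at 2.65 survives the adjustment in nearly every scenario. The losses in step 3 arise only if the sponsor's pairing of 90% with 2.65 is accepted, which implies an SD about twice as large. They also rest on an assumed false discovery rate and an assumed share of changed genes. This objection stands against any unconditional claim of low power. It does not rescue the sentence: at the SD that preserves power at 2.65, the 90% point is 1.64. At either SD, the 90% point rises after adjustment.

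A reader might also infer that a non-significant gene would be taken as evidence of no difference. Nothing in the plan says so. It plans gene-set, pathway and correlation analyses alongside the gene-level tests.

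**Conclusion.** The level in the power statement does not match the planned analysis, whichever SD is used. The size of the consequence at a fold change of 2.65 is conditional. With the implied SD of 1.34 and an assumed 5% false discovery rate, the loss is large, and the 90% fold change moves from 2.65 to about 3.3 to 4.6 at 20 vs 20 when between 20% and 1% of genes differ. With SD 0.68 there is little or no loss at 2.65, but the correct 90% fold change is 1.64 unadjusted and about 1.8 to 2.2 adjusted. Under either reading, 2.65 is not the detectable fold change for the planned analysis. The unstated SD is the more basic gap, because it decides which reading applies.

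The comparison is labelled exploratory and the primary binomial test is untouched. This is worth correcting but does not threaten the trial's main conclusion.

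**What to change.** State the log2 SD used and how it follows from the CV of 50%. Then do one of the following:

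- **(a)** Name IL-10, lesional baseline versus healthy, as the single pre-specified mechanistic test at two-sided 5%, outside the Benjamini-Hochberg family.
- **(b)** Keep IL-10 within the adjusted analysis and restate the detectable fold change at a stated false discovery rate and an assumed share of changed genes, preferably over a range of shares.

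In either case base the figure on 25 baseline patient samples versus 20 controls. For a single 5% test at SD 1.34 this gives a fold change of 2.51.

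The cost is wording only, with no extra patients or samples. Under (a) the power claim covers one transcript and says nothing about the wider screen. Under (b) the detectable fold change is larger than for a single 5% test at the same SD.

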- SD clinical assessments (IGA, SD Severity Score)
- Urine pregnancy test for all female subjects of child-bearing potential
- Collect blood samples for CBC with differential, Comprehensive metabolic panel (CMP), and C-reactive protein (CRP)
- Collect blood sample for possible future mechanistic analyses
- Urinalysis
- Perform tape strips of lesional skin. Lesional skin tape strips will be taken from the same location as the lesional tape strips taken at Baseline and Week 2.
- Assess study drug dosing compliance and retrieve all remaining study drug from subject. Subjects will report each study drug application, with 4 missed doses from Week 2 considered non-compliance.

Visit 5 – Week 6

- Record concomitant medications and adverse events
- DLQI questionnaire

- Standardized clinical photography including photographs of subject's entire face and close up photographs of the following facial regions: 1. Left cheek, 2. Right cheek, 3. Forehead and glabella)
- SD clinical assessments (IGA, SD Severity Score)
- Urine pregnancy test for all female subjects of child-bearing potential
- Perform tape strips of lesional skin. Lesional skin tape strips will be taken from the same location as the lesional tape strips taken at Baseline, Week 2, and Week 4.

Early Termination Visit (if applicable)

- Record concomitant medications and adverse events
- DLQI questionnaire
- Standardized clinical photography (including photographs of subject's entire face and close up photographs of the following facial regions: 1. Left cheek, 2. Right cheek, 3. Forehead and glabella)
- Urine pregnancy test for all female subjects of child-bearing potential
- Collect blood samples for CBC with differential, Comprehensive metabolic panel (CMP), and C-reactive protein (CRP)
- Collect blood sample for possible future mechanistic analyses
- Urinalysis
- SD clinical assessments (IGA, SD Severity Score)
- Perform tape strips of lesional skin. Lesional skin tape strips will be taken from the same location as the lesional tape strips taken at Baseline and Week 2 (if applicable)
- Assess study drug dosing compliance and retrieve all remaining study drug from subject

For Control Subjects

Visit 1 – Screening (within 28 days of Baseline)*

- Obtain signed IRB-approved informed consent and HIPPA agreement
- Review Inclusion and Exclusion Criteria
- Record gender, race, ethnicity, and medical history
- Review personal and family medical conditions/diseases

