An "Initial Pregnancy Report" or equivalent must be completed in full and emailed to [contact] or faxed to [name] within 24 hours of discovery of a pregnancy of a subject who has taken the Incyte product or the pregnancy of a partner for a subject who has taken the Incyte product. The "Follow-up Pregnancy Report Form" or equivalent must be completed and emailed to [contact] or faxed to [name] within 30 days after delivery, so that Incyte is provided with information regarding the outcome of the pregnancy. If the pregnancy results in any events which meet the serious criteria (i.e., miscarriage or termination), the SAE reporting process needs to be followed and the timelines associated with a SAE should be followed.

SUBJECT IDENTIFICATION

Subjects are numbered sequentially. Each subject will be assigned a unique screening number for the duration of the study. Subject screening numbers will not be reassigned or reused for any reason. The investigator must maintain a master log linking the subject number to the subject's name. The investigator must follow all applicable privacy laws in order to protect a subject's privacy and confidentiality.

STUDY DRUG SUPPLY:

Seborrheic Dermatitis Ruxolitinib Cream Protocol
Incyte IIR
March 25, 2022

Eligible patients will receive a supply of ruxolitinib 1.5% cream which they will apply to affected skin on the face only twice daily. Patients will be instructed not to use more than 60g of cream per week.

All study medication will be stored in a secure cool area between 15-30°C. Study drug will be provided to subjects at each study visit, with initial application performed at that time and subsequent applications performed by the patients at home.

Subjects will be queried during each study visit on any missed applications.

STATISTICAL CONSIDERATIONS:

Sample Size Calculation

A sample size of n=20 SD patients guarantees 90% power at 2.1% significance to detect a minimum proportion of 75% of patients with IGA 0/1 at week 4. This calculation assumes the application of the one-sided binomial test with a null hypothesis proportion of 40%. This proportion is based on the vehicle response benchmark reported by Zirwas et al.(2021) when comparing IGA 0/1 at week 8 in 154 patients treated with roflumilast foam 0.3% vs. 72 patients in the vehicle-controlled group(18). Accounting for a 20% dropout rate, we, therefore, propose a sample size of n=25 patients.

Mechanistic Endpoint

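### The Week 6 versus Week 4 change in overall severity score is a stated secondary endpoint but has no planned analysis

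*Combined protocol and SAP*

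**What the plan says.** In the plan SD means seborrheic dermatitis; below, standard deviation is written out.

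- **Secondary Endpoints:** "Change in overall clinical SD at 6 weeks (i.e., 2 weeks after treatment cessation) from baseline and from 4 weeks". This gives two contrasts for the Week 6 score.
- **Analysis of Secondary Endpoints:** "The two-sided paired t-test will assess the significance of changes from baseline in", followed by a list that includes "Overall clinical SD scoring at 4 and 6 weeks of treatment". Both contrasts in this list use baseline as the reference.
- **Same section, multiplicity:** "The p-values will be adjusted by the Bonferroni method". No alpha, test count or family is given. The lists above that sentence hold six efficacy tests (IGA, three score components, and the overall score at two visits), the vital signs, and "Analytes measured in interval or ratio scale from laboratory tests (hematology, serum, chemistry, and urinalysis) at 4 weeks of treatment".
- **Procedures and Table 1:** the severity score is recorded at both Week 4 and Week 6. At Week 4 staff are to "Assess study drug dosing compliance and retrieve all remaining study drug from subject", so the interval from Week 4 to Week 6 is off treatment.

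**The concern.** Followed as written, the plan produces two from-baseline tests of the overall score and nothing on the change between Week 4 and Week 6. Those two tests do not answer the off-treatment question, because both can be significant whether the benefit was kept or half of it was lost. If the same patients attend both visits, a reader could subtract the two reported means. The precision of that difference would still be unknown, because it depends on the correlation between the two changes.

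A second, smaller matter sits in the same paragraph. Bonferroni needs a test count, and the plan does not say whether vital signs and laboratory analytes share a family with the efficacy tests. The count affects power for moderate effects.

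**Working it through.** **1. The plan's own figure.** The only related calculation is for the primary test: one-sided binomial, 40% versus 75%, n=20, which "guarantees 90% power at 2.1% significance". The exact rule of at least 13 responders in 20 gives alpha 0.0210 and power 0.898, and 20/(1-0.20) = 25. Both agree with the plan. There is no corresponding figure for the secondary endpoints.

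**2. Does any other section cover the contrast?** The Spearman analysis uses changes from baseline at Week 4. The mixed models are for gene and protein data. The amendment log mentions a model of the score over Weeks 0, 2, 4 and 6, but that text is superseded. Nothing current covers it.

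**3. Can the planned tests stand in?** Assumptions, none from the plan except n=20 (its number after dropout): each change from baseline has standard deviation 1, the improvement is 2.0 at Week 4 and 1.0 at Week 6, and the family alpha is two-sided 5%, so each test uses 0.05/m. Power is from the noncentral t with 19 degrees of freedom and noncentrality d√20. The Week 4 test has about 100% power, so the Week 6 test (d = 1.0) decides whether both are significant: 92% with m=6, 77% with m=30, 71% with m=50. If nothing is lost, both are significant in about 100% of trials. The usual result is the same pair of significant tests in either case.

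**4. What would the missing contrast deliver?** With correlation ρ between the two changes, the standard deviation of the within-patient difference is √(2(1-ρ)), so d = loss/√(2(1-ρ)).

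| Loss, ρ | d | Power at 0.05/7 | Power with 31 to 51 tests |
|---|---|---|---|
| 1.0, 0.3 | 0.845 | 77% | 55% to 48% |
| 1.0, 0.5 | 1.000 | 91% | 77% to 71% |
| 1.0, 0.7 | 1.291 | 99% | 97% to 95% |
| 0.5, 0.3 | 0.423 | 17% | lower still |
| 0.5, 0.5 | 0.500 | 25% | lower still |
| 0.5, 0.7 | 0.645 | 47% | lower still |

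Seven is the six listed efficacy tests plus this one. The range 31 to 51 assumes 24 to 44 safety variables in the same family. The 95% CI half-width is 2.093/√20 = 0.468 standard deviations of the difference, whatever the true loss.

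**5. Effect of the undefined family.** At 0.8 standard deviations, n=20 and alpha 5%, power for one paired t-test is 73% (m=6), 71% (m=7), 49% (m=30) and 42% (m=50). At 1.2 it is still 93% (m=30) and 90% (m=50).

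**6. Holm against Bonferroni.** Simulated average power over seven efficacy tests, all treated as paired t-tests, correlation 0 to 0.7:

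- 0.8 standard deviations, efficacy as its own family: about 71% rises to 82%-87%, a gain of 11 to 16 points.
- 0.8, with null safety tests pooled: about 48% to 50% (31 tests) and 41% to 42% (51 tests).
- 1.2: 98.5% to 99.9% (7 tests), 93% to 94% (31), 90% to 91% (51).

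**The case against.** The strongest reply concedes the omission and disputes what might be built on it. Three stronger readings that a reader might infer do not hold.

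- **That Bonferroni is a mistake.** It is a valid adjustment. Holm's sizeable gain requires both moderate effects and efficacy tests in their own family, and the plan does not define that family. The design target points to larger effects. If 75% of patients drop exactly 2 IGA points and the rest do not change, the mean change is 1.5 with standard deviation 2√(0.75×0.25) = 0.866, or 1.73 standard deviations. With 40% responders, the primary null, it is 0.8/0.980 = 0.82. If the 25% non-responders instead worsen by 1 point, it is 1.25/1.299 = 0.96. So 0.8 lies near the unfavourable end.
- **That the secondary alpha is unknowable.** The 2.1% is the attained level of the exact primary rule. The only two-sided level in the documents is 5%, in the IL-10 sample size under Mechanistic Endpoint. Stating 5% for the secondary tests would supply a missing detail; it would not settle a contradiction.
- **That the added test would reliably detect relapse.** The 77% to 99% range needs a 1.0 standard deviation loss and a seven-test family. Outside those conditions power can be low, so the estimate and its interval matter more than the p-value.

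All three limits stand. None of them fills the gap between the endpoint list and the analysis section. The phrase about six weeks of treatment is only a wording slip, since the endpoint list already places Week 6 after cessation.

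**Conclusion.** The point holds in a narrow form. One of the two contrasts in a stated secondary endpoint has no planned analysis, and the two from-baseline tests do not replace it. This rests on the text alone and is secure. The power figures are illustrations: they assume effect sizes, correlations, a two-sided 5% family alpha, 24 to 44 safety variables, and the paired t-test as a stand-in for the Wilcoxon tests. The missing alpha and family definition are missing detail, and Holm is an optional improvement. Severity is minor: these are secondary tests in an open-label, single-arm study, and the primary test and conclusions about large effects are unaffected.

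**What to change.** 1. Add to the paired t-test list in the Analysis of Secondary Endpoints the overall severity score at Week 6 versus Week 4, in patients with both visits, reported mainly as mean change with 95% CI.
2. In the same paragraph, state the secondary alpha (for example two-sided 5%) and list the tests in the family, including this seventh efficacy test. The sponsor should say whether vital-sign and laboratory changes belong to that family.
3. Optionally replace Bonferroni with Holm, which controls the same familywise error and never rejects less. It has no simple matching simultaneous intervals, so label the CIs as unadjusted.
4. Align the wording on Week 6 with the endpoint list, which places that visit after treatment has stopped.

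**Cost:** a few sentences, with no new visits or data. If efficacy is its own family, the seventh test lowers Bonferroni power slightly, from 73% to 71% at 0.8 standard deviations and n=20. If safety tests form a separate 5% family, the error across the two families can reach 10%. If they are instead reported with nominal intervals, 24 to 44 independent null tests give 1.2 to 2.2 expected false positives (24×0.05 to 44×0.05).
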